1. SUMMARY

Residual congestion in hospitalized heart failure (HF) patients at discharge is one of the main causes of early readmission. The ReDS (Remote Dielectric Sensing) system is a non-invasive, easy-to-use, and rapid technique that accurately measures the proportion of fluid in lung tissue using RADAR technology. A pilot clinical trial (3 centers, 100 patients) led by the Principal Investigator (PI) demonstrated that guiding decongestion using the ReDS system during hospitalization was associated with a significant reduction in the 30-day readmission rate compared to standard clinical practice, without associated safety events.

Our current objective is to confirm the efficacy and safety of a ReDS-guided decongestion strategy in hospitalized congestive HF patients. To achieve this, an independent, randomized, single-blind clinical trial has been designed, enrolling up to 1,014 congestive HF patients in 25 Spanish hospitals. Patients will be randomized to a decongestion strategy, hospital discharge, and early follow-up in HF units based on ReDS system values versus a strategy based on current clinical practice. All patients will be evaluated daily during hospitalization and in two post-discharge visits (at approximately 10 and 30 days) in HF units using the ReDS system. However, information will only be available to clinicians in the intervention group.

The primary efficacy endpoint will be all-cause mortality, HF readmission, or HF-related decompensations at 30 days. The primary safety endpoint will be the rate of symptomatic hypotension, electrolyte imbalances, or worsening renal function at 30 days.

2. BACKGROUND AND REFERENCES

Heart failure (HF) is a growing epidemic and a public health priority. Specifically, decompensated HF is the most common cause of hospitalization in individuals over 65 years old and is associated with high morbidity and mortality rates (1,2). Despite advances in pharmacological treatment and the development of HF units for early and close follow-up, readmission rates remain unacceptably high (3).

Congestion is a key feature in the pathophysiology of acute decompensated HF, and residual congestion at hospital discharge significantly contributes to the risk of readmission (3,4). Traditionally, congestion has been assessed non-invasively through symptoms and signs, as well as other tools such as chest X-rays, plasma natriuretic peptide levels, and echocardiography (5). However, these methods are subject to significant interobserver variability and may not be reliable for various reasons.

In recent years, managing congestion using implantable pulmonary artery pressure sensors that provide real-time hemodynamic measurements has been shown to reduce HF readmissions (6). Unfortunately, due to their invasive nature and high cost, their expansion has been very limited.

Therefore, developing non-invasive volume assessment methods to aid in HF management and identify a "euvolemic" state is an attractive concept, particularly during hospitalization and shortly after discharge—a vulnerable period for recurrent congestion and readmission (7,8). Various alternative techniques to traditional congestion parameters have emerged in recent years, including clinical scores, novel analytical biomarkers, ultrasound techniques, and the ReDS system, which uses electromagnetic energy to measure pulmonary fluid content accurately and non-invasively (17).

Observational studies—some conducted by the PI—have shown that ReDS-guided treatment has the potential to reduce HF readmissions when used in a post-discharge follow-up setting (18,19). Our group recently led the first randomized, single-blind clinical trial evaluating the efficacy and safety of a ReDS-guided decongestion strategy in hospitalized HF patients. This independent, multicenter, international pilot study demonstrated that this strategy significantly reduced the 30-day HF readmission rate without compromising patient safety (20). However, the relatively small sample size suggests caution in interpreting its findings as "proof of concept." Therefore, a study designed to confirm these promising results with sufficient statistical power, allowing subgroup analyses and assessing feasibility across a broader range of centers, is urgently needed.

References

- 1. McDonagh TA et al. 2021 ESC Guidelines for the diagnosis and treatment of acute and chronic heart failure. Eur Heart J. 2021 Aug 27; ehab368.
- 2. van Riet EES et al. Epidemiology of heart failure: the prevalence of heart failure and ventricular dysfunction in older adults over time. A systematic review. Eur J Heart Fail. 2016 Mar;18(3):242–52.
- 3. Kociol RD et al. Markers of decongestion, dyspnea relief, and clinical outcomes among patients hospitalized with acute heart failure. Circ Heart Fail. 2013 Mar;6(2):240–5.
- 4. Lala A et al. Relief and Recurrence of Congestion During and After Hospitalization for Acute Heart Failure: Insights From Diuretic Optimization Strategy Evaluation in Acute Decompensated Heart Failure (DOSE-AHF) and Cardiorenal Rescue Study in Acute Decompensated Heart Failure (CARESS-HF). Circ Heart Fail. 2015 Jul;8(4):741–8.

- 5. Gheorghiade M et al. Assessing and grading congestion in acute heart failure: a scientific statement from the acute heart failure committee of the heart failure association of the European Society of Cardiology and endorsed by the European Society of Intensive Care Medicine. Eur J Heart Fail. 2010 May;12(5):423–33.
- 6. Abraham WT et al. Wireless pulmonary artery haemodynamic monitoring in chronic heart failure: a randomised controlled trial. Lancet. 2011 Feb 19;377(9766):658–66.
- 7. Picano E et al. Why, when, and how to assess pulmonary congestion in heart failure: pathophysiological, clinical, and methodological implications. Heart Fail Rev. 2010 Jan;15(1):63–72.

3. HIPOTHESIS

1. Primary:

1.1. A ReDS-guided decongestion strategy to assess pulmonary congestion during hospitalization for HF will help optimize patients before discharge and during early outpatient follow-up, improving short-term prognosis (1 month).

2. Secondary:

- 2.1. A ReDS-guided decongestion strategy will be particularly beneficial for patients in whom pulmonary congestion is difficult to estimate (e.g., obesity, renal insufficiency, diuretic resistance).
- 2.2. ReDS values will positively correlate with plasma natriuretic peptide and CA125 levels, with a greater reduction of both biomarkers in patients assigned to a ReDS-guided decongestion strategy.
- 2.3. A ReDS-guided decongestion strategy will be as safe as standard management in terms of symptomatic hypotension, electrolyte imbalances, and/or worsening renal function.
- 2.4. A ReDS-guided decongestion strategy will be cost-effective from the national healthcare system perspective.

4. OBJECTIVES

1. Primary:

1.1. To evaluate whether a ReDS-guided decongestion strategy during hospitalization for HF and early outpatient follow-up is superior to standard clinical practice in reducing the combined event rate of all-cause mortality, HF readmission, or HF visits requiring diuretic adjustment at one month.

2. Secondary:

- 2.1. To analyze the efficacy of a ReDS-guided decongestion strategy in specific clinically relevant subgroups (obesity, chronic renal insufficiency, diuretic resistance) and epidemiological subgroups (age and sex).
- 2.2. To correlate ReDS system measurements with plasma natriuretic peptide and CA125 levels at admission, discharge, and outpatient follow-ups.
- 2.3. To determine the safety of a ReDS-guided decongestion strategy compared to standard clinical practice at one-month post-discharge by evaluating renal function deterioration, symptomatic hypotension, and electrolyte imbalances.
- 2.4. To calculate the cost-effectiveness of a ReDS-guided decongestion strategy considering hospital stay duration and reduction of the combined efficacy endpoint.

5. METHODOLOGY

5.1. Study design (annex 1)

A randomized, single-blind, controlled, multicenter clinical trial (list of investigators and participating centers in annex 2) promoted by the researcher, which evaluates the efficacy and safety of a decongestion strategy guided by the ReDS system compared to standard clinical practice in patients admitted for decompensated heart failure.

5.2. Study population

Those adult patients meeting all the following criteria will be included:

- 1. Hospitalized due to HF as the main reason, including the presence of symptoms and signs of congestion, regardless of the left ventricular ejection fraction (LVEF).
- 2. NT-proBNP greater than 1000 pg/L or BNP greater than 300 pg/L upon admission.

Patients meeting any of the following conditions will be excluded:

- 1. Height less than 150 cm or greater than 190 cm or body mass index (BMI) less than 22 or greater than 39, conditions where the use of ReDS is not approved.
- 2. Patients requiring inotropes or vasopressors upon admission, with mechanical support, or heart transplant recipients.
- 3. Any malformation or variant affecting the right lung anatomy (e.g., a pacemaker).
- 4. Patients with any heart disease requiring a planned surgical intervention during the clinical trial (coronary disease, valve disease, or other).
- 5. Chronic kidney disease on hemodialysis.
- 6. Life expectancy less than 12 months due to non-cardiological origin.
- 7. Participation in another clinical trial with intervention.

5.3. Variables

- 1. Primary efficacy variable: combined 30-day outcome of all-cause mortality, heart failure (HF) readmission, or HF-related visits requiring diuretic treatment adjustment.
- 2. Secondary efficacy variable: individual components of the main variable, proportional change in natriuretic peptides and CA125 between admission and the first post-discharge outpatient visit, New York Heart Association functional class at the first post-discharge outpatient visit, average length of stay, cost of hospitalization for HF, and unplanned visit.
- 3. Primary safety variable: combined outcome of symptomatic systolic hypotension (<90 mmHg), electrolyte imbalances (potassium below 3 or above 5.5 meq/L), and/or worsening of renal function compared to the baseline visit at the first post-discharge outpatient visit (at least 50% reduction in glomerular filtration rate).
- 4. Secondary safety variables: individual components of the primary safety variable.
- 5. Cost-effectiveness variables: average length of stay and cost of the ReDS device.

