5.4. Protocol

Patients will be identified and selected upon admission. If they meet the selection criteria and confirm their willingness to participate in the study, they will be randomized in a 1:1 sequence through a mobile application specifically designed for the study by P INVESTIGA, to one of the following interventions within 48 hours of hospital arrival:

1) "ReDS-guided strategy." Each day, the clinician responsible for the patient will have access to the ReDS value and will adjust the treatment according to the study's diuretic protocol (annex 3). The responsible physician can discharge the patient if the clinical stability criteria are met, and the ReDS value is below 35% and/or a reduction of 15% or more from the admission ReDS value has been achieved. If the ReDS criteria are not met, the patient must remain hospitalized for another day until these conditions are met. Clinical stability is defined as the presence of at least 2 of the following 3 conditions: i) discharge weight lower than admission weight, ii) at least a 20% reduction in natriuretic peptide from admission, and iii) a score <2 in the Orthoedema score.

2) "Usual clinical practice strategy." The responsible physician will not have access to the ReDS values and will adjust the treatment according to their clinical judgment and local practices. Discharge can be given if the clinical stability criteria are met.

The ReDS technology has been described in detail previously (7, 8, 20). Briefly, the ReDS system consists of 2 sensors that are placed (sitting or supine) on the front (infraclavicular) and back (below the scapula) of the patient's right hemithorax and in 45 seconds accurately quantifies the proportion of fluid in the lung. The sensors are connected via 1 cable to a touchscreen monitor that easily guides the measurement process and stores this information. The accuracy of this technology has been validated with high-resolution chest computed tomography (8) and invasive hemodynamic measurements with a Swan-Ganz catheter (9). Normal ReDS values range between 20% and 35% (i.e., 20-35% of the lung would be fluid). Above 35% is considered congestive, whereas below 20% the lung would be "dry" or dehydrated.

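### Inclusion criterion 2 gives its natriuretic-peptide thresholds in pg/L, 1000 times lower than the same figures in pg/mL, and nothing else in the protocol corrects the unit

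*Protocol*

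**What the plan says.** Protocol Section 5.2 (Study population) opens its inclusion list with "Those adult patients meeting all the following criteria will be included", so every listed criterion is mandatory. There are two.

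- Criterion 1 is clinical: "Hospitalized due to HF as the main reason, including the presence of symptoms and signs of congestion", at any ejection fraction.
- Criterion 2 is the laboratory threshold: "NT-proBNP greater than 1000 pg/L or BNP greater than 300 pg/L upon admission".

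Seven exclusion criteria follow. None involves a natriuretic peptide.

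Elsewhere the peptides appear without a unit or an absolute level. Section 5.3 lists their proportional change as a secondary efficacy variable. Section 5.4 uses a relative rule within the definition of clinical stability, "at least a 20% reduction in natriuretic peptide from admission". Section 5.5 names NT-proBNP/BNP among the blood tests at baseline, at discharge and at both outpatient visits.

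**The concern.** A numeric entry threshold is there to separate patients who should enter from patients who should not. Expressed in pg/L, the two figures are so small that they are unlikely to do this in people already in hospital with congestive heart failure. In pg/mL or ng/L the same figures could work as a threshold, which is why a slip of unit is the likely explanation.

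What is at stake is the operative eligibility rule at 25 hospitals. Take a patient with NT-proBNP of 200 pg/mL, a value chosen only for illustration. That is 200,000 pg/L, so the patient passes the criterion as written but fails it if the figure is meant in pg/mL. Section 5.13.1 treats any failure to follow the plan's requirements as a deviation, and Section 6 has monitors check adherence to the protocol. With the present text they cannot say whether enrolling this patient is correct.

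**Working it through.** **Inputs**, all from Section 5.2, inclusion criterion 2:

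- NT-proBNP threshold: 1000 pg/L
- BNP threshold: 300 pg/L

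The protocol states these as given values without a derivation, so there is no calculation of its own to reproduce.

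**Conversion.** 1 L = 1000 mL, so x pg/L = x/1000 pg/mL. Also 1 ng = 1000 pg, so 1 pg/mL = 1000 pg/L = 1 ng/L.

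| Marker | As written | In pg/mL (= ng/L) | Same number meant in pg/mL | Ratio |
|---|---|---|---|---|
| NT-proBNP | 1000 pg/L | 1000/1000 = 1.0 | 1000 pg/mL = 1,000,000 pg/L | 1,000,000/1000 = 1000 |
| BNP | 300 pg/L | 300/1000 = 0.3 | 300 pg/mL = 300,000 pg/L | 300,000/300 = 1000 |

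**Is the unit corrected elsewhere?** Sections 5.3, 5.4 and 5.5 are the other places in the main text where the peptides are measured or used. They give proportional changes or list the test, with no unit and no level. A relative reduction is free of units, so it cannot settle the question.

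**Could it be a reading fault?** The unit is printed twice in the line, once per marker, and is the same both times. A stray character is therefore unlikely, though a fault in reading the PDF cannot be fully ruled out.

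**Does it reach the sample size?** Section 5.6 plans 507 per group for a 15% event rate halved, with 80% power, 5% alpha and 10% loss. Suppose, purely as an assumption, that lower-risk entrants brought the control rate down to 10%, again halved. With two-sided alpha and unpooled variances:

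n per group = (1.960 + 0.842)² × [p₁(1 − p₁) + p₂(1 − p₂)] / (p₁ − p₂)², where (1.960 + 0.842)² ≈ 7.849 using unrounded normal quantiles.

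- 15% vs 7.5%: 7.849 × (0.1275 + 0.069375)/0.005625 = 274.7, about 275.
- 10% vs 5%: 7.849 × (0.0900 + 0.0475)/0.0025 = 431.7, about 432.
- 10% vs 5%, allowing for loss: 431.7/0.9 = 479.7, about 480, which is below 507. Equivalently, 507 × 0.9 = 456 evaluable, above 432.

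The margin is modest and depends on the formula. The pooled-variance formula gives 435, or 435/0.9 = 483.3. Adding a continuity correction, n/4 × [1 + √(1 + 4/(n × 0.05))]² with n = 435, gives about 474, or 474/0.9 = 526.7, slightly above 507.

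**The case against.** The strongest reply is that this is a slip that no one would act on. A heart failure team will probably read 1000 and 300 in its own laboratory's unit, so the rule would work as intended. That is plausible and limits the likely practical effect to an ambiguous rule. It does not remove the fault, because the written protocol is what monitors check against, and it supplies no second statement of the threshold.

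The remaining objections concern how far the consequences reach, and most of them stand.

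- A reader might infer that patients without heart failure could be randomised. The documents do not support this. Even if criterion 2 had no effect, criterion 1 would still require an admission mainly for heart failure with symptoms and signs of congestion, and the seven exclusions would still apply.
- A reader might infer that the study app would enforce the wrong threshold automatically. Sections 5.4 and 5.5 describe the app for randomisation and data capture. They do not describe an eligibility screen with a coded peptide threshold.
- A reader might infer a lower event rate and a loss of power. Section 5.6 takes its 15% from the participating hospitals' average in 2023 and does not say that those patients were selected by a peptide level. A fall to 10% therefore has no basis in the protocol. By the formula shown, the planned 507 per group would in any case cover 10% versus 5%.
- That the criterion would screen out essentially no one is itself an inference, because the protocol gives no distribution of peptide values.

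**Conclusion.** The unit is wrong as written, or at the least cannot be what was intended, in a mandatory eligibility rule. The size is exact: a factor of 1000 for each marker, giving 1 pg/mL for NT-proBNP and 0.3 pg/mL for BNP.

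The statement that criterion 2 would exclude essentially no one holds for the literal reading only. It assumes that patients admitted with congestive heart failure have values well above those levels, and it concerns criterion 2 alone, not the whole selection of patients. That pg/mL or ng/L was intended is likely but is for the sponsor to confirm.

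No claim is made about a diluted effect, a lower event rate or an inadequate sample size. The point warrants correction because the threshold is operative, is corrected nowhere else and is simple to put right.

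**What to change.** The sponsor should confirm the unit intended for each marker and correct inclusion criterion 2 in Section 5.2 for both NT-proBNP and BNP. It should then check whether the study app or the electronic case report form holds any eligibility field or range check for these peptides and, if so, make it use the same unit. If any patient was accepted on the literal pg/L reading, that patient's eligibility should be reviewed; the protocol does not show that this has happened.

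The cost is one corrected line and one configuration check, handled through the amendment procedure in Section 5.13. The sample size does not need to change on account of this point.

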5.5.1 Baseline visit (within first 48 hours of hospital admission)

- Informed consent with date and signature of the patient and local investigator.
- Demographic data: race, gender, and age, and anthropometric data: weight and height.
- Complete medical history, including main comorbidities and usual medical treatment.
- Usual NYHA functional class before decompensation.
- Vital signs (blood pressure, heart rate, arterial saturation) and daily physical examination findings (weight, signs of left and right congestion).
- 12-lead ECG.
- Baseline echocardiogram (or the last available in the year before the current admission).
- Complete blood tests (renal and liver function, electrolytes, lipid profile, NTproBNP/BNP, CA125, blood count, and coagulation).
- Alternative methods for congestion analysis used by local clinical practice: lung ultrasound, VExUS, impedance, right heart catheterization.
- Measurement with the ReDS system.

5.5.2. Follow-up visits (every day during admission):

- Vital signs (blood pressure, heart rate, arterial saturation) and daily physical examination findings (weight, signs of left and right congestion).
- Measurement with the ReDS system
- Alternative methods for congestion analysis used by local clinical practice: lung ultrasound, VExUS, impedance, right heart catheterization.

5.5.3. Visit at discharge (within 24 hours before hospital discharge):

- Current NYHA functional class at discharge.
- Vital signs (blood pressure, heart rate, arterial saturation) and daily physical examination findings (weight, signs of left and right congestion).
- 12-lead ECG.
- Echocardiogram at discharge (not mandatory).
- Complete blood tests (renal and liver function, electrolytes, lipid profile, NTproBNP/BNP, CA125, blood count, and coagulation).
- Alternative methods for congestion analysis used by local clinical practice: lung ultrasound, VExUS, impedance, right heart catheterization.
- Measurement with the ReDS system
- Major interventions performed during the index admission: revascularization, electrical cardioversion, arrhythmia substrate ablation, device implantation, complications, etc.

5.5.4. First visit at HF Clinic (14 +/- 3 days after hospital discharge):

- Current NYHA functional class.
- Vital signs (blood pressure, heart rate, arterial saturation) and daily physical examination findings (weight, signs of left and right congestion).
- 12-lead ECG.

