Annex 3: ReDS guided diuretic protocol

ReDS (%)	Diuretic Protocol
Less than 20%	Discontinue diuretics.
20-35%	Maintain the prescribed diuretic dose. Consider switching from intravenous to oral administration if no significant edema is present. If significant edema persists, continue intravenous.
36-45%	Increase the diuretic dose. Switch to intravenous administration if given orally. Add a thiazide diuretic if the intravenous dose is equivalent to 200 mg.
Greater than 46%	Add a second diuretic. Administer all diuretics intravenously and aim for an hourly diuresis of at least 250 ml in the next 2 hours. If this is not achieved, double the prescribed dose.

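### The visit component of the primary endpoint is not tied to worsening heart failure, so a ReDS-prompted diuretic change at a scheduled clinic visit can count as an event in one arm only

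*Protocol*

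**What the plan says.** Protocol section 5.3 gives the primary efficacy variable as "combined 30-day outcome of all-cause mortality, heart failure (HF) readmission, or HF-related visits requiring diuretic treatment adjustment". The primary objective in section 4 matches it: "all-cause mortality, HF readmission, or HF visits requiring diuretic adjustment at one month". The Summary words the third component differently: "The primary efficacy endpoint will be all-cause mortality, HF readmission, or HF-related decompensations at 30 days".

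The randomized strategy continues after discharge. The Summary describes "early follow-up in HF units based on ReDS system values versus a strategy based on current clinical practice". ReDS is measured in every patient at two scheduled clinic visits. Section 5.5.4 sets the "First visit at HF Clinic (14 +/- 3 days after hospital discharge") and section 5.5.5 sets the final visit at day 30 ± 5. The Summary restricts access to the values to clinicians in the intervention arm.

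The only rule in the protocol that turns a ReDS value into treatment is Annex 3. For a reading of 36–45% it says "Increase the diuretic dose. Switch to intravenous administration if given orally". It also calls for a change below 20% and for no dose change between 20% and 35%. Section 5.4 invokes Annex 3 for daily care during the admission.

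Sections 5.9 and 7.5 provide for a clinical events committee, and section 5.9 has events reviewed blind to study group. Neither section says how a diuretic change at a scheduled visit, or one prompted by a ReDS reading, is to be classified.

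**The concern.** An outcome should measure what the strategy achieves. Here one component is a treatment action that the strategy itself can prompt. As sections 4 and 5.3 are worded, three things are left unrestricted: the reason for the visit, the reason for the change, and its direction.

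The information behind the action differs by arm. A ReDS-arm clinician who sees a high reading at the first clinic visit has a reason to change the diuretic. A control-arm clinician facing the same lung fluid has only the clinical picture. The component is thus ascertained differently by arm, on the primary endpoint.

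If enough reading-driven changes are counted, a strategy that truly reduces death and readmission could look ineffective. The interim looks at 30% and 60% of the sample (sections 5.6 and 5.8), which are meant to detect futility, would be affected in the same way.

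**Working it through.** **Step 1. The wording.**

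| Place | Third component | Limited to worsening HF? | Limited to intensification? |
|---|---|---|---|
| Summary | decompensations | by implication | no |
| Section 4 | HF visits with a diuretic adjustment | no | no |
| Section 5.3 | HF-related visits with a diuretic adjustment | no | no |

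The first clinic visit (days 11 to 17) always falls within 30 days of discharge. The final visit (days 25 to 35) may. The discharge rule in section 5.4 accepts either a value below 35% or a fall of at least 15%. If that fall is read as relative, a patient going from 45% to 38% qualifies (7/45 = 15.6%). ReDS-arm patients can therefore leave hospital with a value that Annex 3 treats as calling for a change.

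**Step 2. The plan's own figure.** Section 5.6 gives 15% control risk, a 50% reduction, 80% power, 5% alpha and 10% loss, and states 507 per group. The usual two-proportion formula, two-sided, gives

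n = [1.960·√(2·0.1125·0.8875) + 0.842·√(0.15·0.85 + 0.075·0.925)]² / 0.075² ≈ 278 per group,

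and 278/0.9 ≈ 309 with loss. The stated 507 is not reproduced. That is a separate matter. The stated size, 507 × 0.9 = 456 evaluable per group, has about 95% power for 15% versus 7.5%, so the check below starts from a trial with power to spare.

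**Step 3. Effect of counted scheduled-visit changes.** Two shares are needed, and the protocol gives neither. Both are assumptions:

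- q: share of otherwise event-free ReDS patients with a counted change at a scheduled visit.
- c: the same share among otherwise event-free controls.

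Observed risks: ReDS = 0.075 + 0.925·q; control = 0.15 + 0.85·c. Power is for the two-sided 5% pooled z-test with 456 per arm, for a result favouring ReDS.

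| c | q | Control | ReDS | Power |
|---|---|---|---|---|
| 0 | 0 | 15.0% | 7.5% | 95% |
| 0 | 2% | 15.0% | 9.4% | 74% |
| 0 | 5% | 15.0% | 12.1% | 24% |
| 0 | 8.1% | 15.0% | 15.0% | effect erased |
| 5% | 5% | 19.3% | 12.1% | 84% |
| 5% | 8% | 19.3% | 14.9% | 42% |
| 10% | 8% | 23.5% | 14.9% | 91% |
| 10% | 10% | 23.5% | 16.8% | 72% |
| 10% | 20% | 23.5% | 26.0% | direction reversed |

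With c = 0 the assumed effect disappears at q = 0.075/0.925 = 8.1%. Counting changes in controls moves that point up but does not remove it. At c = 5% it is (0.1925 − 0.075)/0.925 = 12.7%, and at c = 10% it is (0.235 − 0.075)/0.925 = 17.3%.

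**Step 4. Cost of a narrower definition.** With the risk halved and 456 per arm, power is 95% at a 15% control rate, 82% at 10% and 72% at 8%.

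**The case against.** A reader might infer that Annex 3 obliges clinicians to change diuretics at the clinic visits, so that the intervention is bound to generate primary events. The protocol does not say so. Section 5.4 ties Annex 3 to daily care in hospital, its content (route switching, hourly diuresis) reads as inpatient, and sections 5.5.4 and 5.5.5 list only a measurement. No outpatient algorithm is given. What stands is that the Summary and section 4 extend the ReDS-guided strategy to early follow-up and that only one arm's clinicians see the value. That is enough for reading-driven changes to occur and to be counted.

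A reader might also take it that any change counts, including stopping a diuretic. The component speaks of visits that require an adjustment, and the Summary speaks of decompensations, so a narrower intent is possible. The listing of unplanned visits among the secondary variables does not settle it, because the phrase could refer to their cost. But the operative definition in section 5.3 does not state the narrower intent.

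Nor is a bias against ReDS established. Under the same wording, changes in controls at scheduled visits count too, and a reading in the middle band can prevent a change. The c = 0 rows of the table are one end of a range.

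Finally, the blinded committee could resolve this through its charter. That is true if the charter contains a rule. Blinding alone does not help: members unaware of the arm cannot separate a reading-driven change from a clinical one without a criterion.

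**Conclusion.** The concern holds as a defect in the definition of the primary endpoint. The Summary differs from sections 4 and 5.3, and the operative wording allows the intervention itself to trigger an event that is ascertained differently by arm.

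The size is conditional. It depends on the difference between q and c, which the protocol does not give, and on 15% versus 7.5% with 456 evaluable per arm. With no controls counted, 2% in the ReDS arm takes power from 95% to 74%, 5% takes it to 24%, and about 8% erases the effect. With 5% of event-free controls also counted, the figures are 84% at q = 5% and 42% at q = 8%. Bias against ReDS is the likelier direction but is not proven. Because the fault lies in the primary endpoint and is cheap to correct, it should be settled before outcomes are adjudicated.

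**What to change.** Use one definition in the Summary, section 4 and section 5.3. For example: a visit for worsening heart failure symptoms or signs, judged without the ReDS value, with intensification of diuretic therapy, applied identically in both arms at any visit, scheduled or not. Excluding the scheduled visits altogether would be simpler, but it would discard genuine decompensations first found there.

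Add a rule to sections 5.9 and 7.5, or to the committee charter, that ReDS values and allocation are removed from the material the committee reviews. State that diuretic changes prompted only by a ReDS reading, and reductions or stops, are not events. Report them by arm as treatment received. Section 5.4 should also say whether Annex 3 applies at the clinic visits. Which clinical rule should apply there is for the investigators to decide.

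The cost is a wording amendment and a charter line. The statistical cost is that the control rate may fall below the planned 15%. That figure should be rechecked against the narrower definition, since power for a halved risk would be 82% at a 10% control rate and 72% at 8%.
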